8.7. Assignment of Site and Patient Numbers

Each study site selected to participate in this study will be assigned a site number by the Sponsor or designee. The site number will be used to categorize patient data and to identify the site and/or Investigator within study documents. This number will be recorded in the eCRF.

At screening, each patient will be registered in the IWRS and assigned a unique identification number which will stay the same throughout the study, including the open-label extension. Patients who are re-screened will be assigned a new patient number.

8.8. Treatment Compliance

The Investigator or designee should assess the patient's compliance with study medication dosing at each visit after Day 1. Study medication compliance is defined as the ratio of the number of actual capsules/tablets taken over the number of capsules/tablets that should have been taken during the dosing period multiplied by 100. Patients will be asked to return all unused study medication and used and unused packaging at each visit. If the Investigator has concerns about a patient's dosing compliance, he/she should reiterate the dosing requirements to the patient, and the discussion should be documented in the source documents.

9. STUDY ASSESSMENTS

9.1. Schedule of Study Events

The schedule of study events is located in [Section 15.1](#).

If an on-site visit by the patient is not feasible due to challenges related to the COVID-19 pandemic or other unexpected circumstances, Investigators/appropriately designated study staff will be allowed to perform study visits as remote study visits (eg, conducted via telephone, video conference). These contacts will be allowed at all protocol-required visits and at any time during the conduct of the study. However, Screening (Week 6), Washout (Week 1), and Day 1 (Randomization) visits must be conducted at the study site. The sites will discuss the patient's current health status, AEs, concomitant medications, and medication compliance during the telephone and video contacts. Patients will be instructed to contact the site personnel with any health concerns. Results of these patient contacts will be fully documented in the patient source documents/health records. Patients will return for an on-site visit as soon as the site and the patient determine that it is appropriate and safe.

Given the importance of ongoing laboratory and clinical tests for safety evaluations and to reduce the burden on the patient to come to the clinical site, the Sponsor is contracting with a home care agency to assist with study visits. Dictated by local public health authority requirements and if an Investigator agrees with the patient to utilize the home care services, a signed consent/assent form for home care visits will be obtained at the next site visit. Due to the challenges related to the COVID-19 pandemic or other unexpected circumstances, a verbal consent/assent may be obtained if allowed by local regulations prior to the home care visit and the signed consent/assent form obtained at the next site visit. A licensed nurse will contact the patient or parent/legal guardian via telephone to schedule the home visits in accordance with the Service Request Form provided by the Investigator. In order to conduct the home visits, the home care nurse, the home care agency, and the home care service provider will have access to the patient's personal data including their individually identifiable protected health information, such as the patient's name, address, or telephone number. This type of information will only be used, as necessary, to schedule and conduct the home visits and will not be provided to the Sponsor, the contract research organization, or any other study vendors. Service providers will complete the services ordered by the Investigator, including collection of laboratory samples, and document the service provided in the source documents. Study procedure instructions for the service provider will be provided in the home care visit training manual. Source documentation will be expedited by courier to the study site.

Home care visits may also be utilized for patient retention during the double-blind and the open-label extension periods in any situation that interrupts safety oversight.

Study sites may implement home blood pressure monitoring to allow for further safety assessment. If requested by the Investigator, the Sponsor will supply blood pressure cuffs to the study site to be provided to the patients for monitoring of blood pressure at home. The Investigator will be responsible for instructing the patient about how to monitor and record blood pressure at home.

9.2. Study Fasting Requirements

Beginning on Day 1, all patients must be instructed to arrive at the study site for their next visit in a fasted state (ie, fasting for at least 8 hours prior to the visit). Water is permitted during the fasting period.

9.3. Screening Assessments

Screening Visit assessments for the double-blind period must be performed within 6 weeks prior to Day 1/Randomization; the screening window begins on the day of the patient's first in-clinic study procedure. Each patient will be registered in the IWRS at screening for the double-blind period and assigned a unique identification number which will stay the same throughout the study (including the open-label extension; see [Section 8.7](#)). Patients who fail screening for any reason may be re-screened up to 2 additional times. Patients who are re-screened will repeat all screening procedures and will be re-registered in the IWRS and assigned a new patient number. Patients will also repeat the informed consent procedure at each re-screening.

9.4. Medical History and Demographics

A complete medical history will be obtained from the patient at screening, along with concomitant medications/therapies (including all immunosuppressive therapies the patient has taken in their lifetime) at enrollment. Demographic characteristics will include age, race, ethnicity, and sex. Race is being collected to accurately calculate eGFR (a primary endpoint).

9.5. Physical Examination

Physical examinations will be performed according to the schedule of study events in [Section 15.1](#). Physical examinations will include assessment of the following body systems: abdomen; cardiovascular; ear, nose, and throat; eyes; hair and skin; lymph nodes; mental status; musculoskeletal; neurological; peripheral edema; and respiratory. Peripheral edema will be assessed using the semi-quantitative scale in Appendix B ([Section 15.2.3](#)).

9.6. Vital Signs

Vital signs, including blood pressure, heart rate, temperature, respiration rate, weight, and height, will be performed according to the schedule of study events in [Section 15.1](#). Height will only be recorded at screening for patients ≥ 18 years of age. For patients < 18 years of age, height will be measured every 6 months after screening until the patient turns 18. Vital signs will be measured prior to phlebotomies for clinical laboratory evaluations.

At all protocol-specified time points, blood pressure will be measured after the patient has been sitting comfortably in a chair for at least 5 minutes prior to obtaining 3 readings, using the same arm for each reading, and the mean of the last 2 readings will be recorded. At the Day 1/Randomization visit, vital signs will be obtained prior to dosing and at 1, 2, 3, and 4 hours after the first dose of study medication.

Measurements of blood pressure intended to detect possible orthostatic hypotension will also be performed at each visit according to US Centers for Disease Control and Prevention guidelines ([US CDC 2017](#)). This should be done after the sitting BP measurements have been taken. Briefly, blood pressure will be measured 3 times: 1 time after the patient has been in a supine

position for 5 minutes, 1 time after the patient has been standing for 1 minute, and 1 time after the patient has been standing for 3 minutes. Heart rate will also be collected each time blood pressure is taken. A decrease in systolic blood pressure of ≥ 20 mmHg or diastolic blood pressure of ≥ 10 mmHg, or the presence of lightheadedness or dizziness during the test is considered abnormal and may justify a change in study drug dose at the Investigator's discretion.

9.7. Electrocardiogram

Twelve-lead ECGs should be conducted after the patient has been resting in a supine position for at least 5 minutes. Assessments will be performed according to the schedule of study events in [Section 15.1](#). ECGs will be performed prior to phlebotomies for clinical laboratory evaluations.

Copies of the ECGs may be required to be sent to a central repository for third party review and analysis.

9.8. Clinical Laboratory Assessments

For the double-blind period (with the exception of the Screening Visit [Visit 1]), patients will be instructed to attend each study visit in a fasted state (ie, fasting for at least 8 hours prior to the visit; water is permitted during the fasting period), preferably in the morning, and patients should remain fasted until their blood samples have been collected. For visits that require fasting, the Investigator or designee will document that the patient has fasted in the source documents. If the patient reports having eaten within 8 hours, the Investigator or designee will document accordingly in the source documents and eCRF and remind the patient that fasting is required before all study visits.

For the open-label extension, it is strongly recommended that patients come to the study visit in a fasted state, and patients should remain fasted until their blood samples have been collected. However, if fasting for 8 hours prior to the visit is not possible, the visit should occur as scheduled and it should be documented in the eCRF that the patient was not fasting.

Routine blood and urine samples for laboratory assessments will be collected at the visits specified in the schedule of study events in [Section 15.1](#). The Investigator will receive the results of this testing from the central laboratory and must determine the clinical significance of any results that are outside of the normal range. All randomized patients with clinically significant abnormal test results will be followed regularly until the values return to normal ranges or until further follow-up is deemed medically unnecessary.

Full instructions concerning the number and type of laboratory samples to be collected at each visit, the necessary collection supplies, required sample volumes, sample collection methods, sample processing, sample labeling, and sample shipping will be provided by the central laboratory, and will be appropriately assembled for the specific evaluations required at each visit.

Patients will be provided kits for the home collection of quantitative urinalysis samples. They will also receive full instructions regarding the proper collection of those samples. If necessary, due to challenges related to the COVID-19 pandemic or other unexpected circumstances, a patient or parent/legal guardian may transport the first morning void samples to the site via courier service for processing and shipment to the central laboratory. If a patient cannot come to the site, safety labs may be tested at a local laboratory. It is the responsibility of the Investigator to document this process in the patient's source documents.

The eGFR during screening period will be determined using the Chronic Kidney Disease Epidemiology (CKD-EPI) equation for adults (Levey 2009) and the Modified Schwartz formula (Schwartz 2009a; Schwartz 2009b) for children <18 years of age.

The eGFR for each timepoint (visit) during the double-blind period will be determined using the CKD-EPI equation for adults (Levey 2009) and children ≥ 16 years of age at screening for the double-blind period, and the Modified Schwartz formula for children <16 years of age at screening for the double-blind period (Schwartz 2009a; Schwartz 2009b). The eGFR for each timepoint (visit) during the open-label extension will be determined using the CKD-EPI equation for adults (Levey 2009) and children ≥ 16 years of age at Week 108, and the Modified Schwartz formula for children <16 years of age at Week 108 (Schwartz 2009a; Schwartz 2009b).

UP/C will be determined using first morning void urine samples. For the double-blind period, UP/C will be calculated as the average of 3 first morning void urine samples collected within 5 days prior to the visit. If 1 of the samples is missing, the average of the other 2 samples will be used. For the open-label extension, UP/C will be based on a single first morning void sample collected within 5 days prior to the visit.

The list of clinical laboratory analytes to be tested is presented in [Section 15.2.4](#).

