6.1.3. Open-Label Endpoints

Endpoints for the open-label extension include, but are not necessarily limited to:

- The absolute and percent change from Week 112 in eGFR at each visit
- The percent change from Week 112 in UP/C at each visit
- Changes from Week 112 in QoL at each visit
- Changes from Week 112 in body weight, vital signs, physical examinations, peripheral edema, and clinical laboratory parameters

- Changes from Week 112 in lipid profile (total cholesterol and triglycerides, LDL-C, and HDL-C)
- The incidence of TEAEs during the open-label extension

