Following a 108-week blinded treatment period, treatment with study medication will be discontinued, and patients may be evaluated for eligibility in the open-label extension using values from the Week 108 visit as screening assessments (see Section 6.2.2). At this time, the Investigator should resume standard-of-care treatment, including treatment with RAAS inhibitors provided there are no contraindications for their use. If the patient was treated with irbesartan at study entry, an alternative ARB at an equivalent dose is required from Week 108 to Week 112. The Investigator may make additional adjustments in antihypertensive medications as necessary to adequately control the patient's blood pressure.

Patients will return to the site for the final visit of the double-blind period 4 weeks after study medication has been discontinued (ie, Week 112; see Figure 1).

Figure 1: Study 021FSGS16010 Overview Flow Chart of the Double-Blind Period

^a Screening may begin after informed consent has been signed. The screening window begins on the day of the patient's first in-clinic study procedure. Patients should be screened within the 6-week screening period; however, under extenuating circumstances the screening period may be extended by a maximum of 2 weeks.

^b For patients who are undergoing washout from RAAS inhibitors.

^c Patients whose body weight is ≤ 50 kg at screening will receive one-half the otherwise specified doses of either sparsentan or irbesartan (active control). Weight will be measured at each visit and the dose increased at the Investigator's discretion if the patient's weight reaches >50 kg.

^d Day 1 events shown will occur in the order in which they are listed.

^e Randomization will be stratified by eGFR value (≥ 30 to <60 mL/min/1.73 m² and ≥ 60 mL/min/1.73 m² for all patients) and UP/C (≤ 3.5 g/g and >3.5 g/g [396 mg/mmol; patients ≥ 18 years of age] or ≤ 2 g/g and >2 g/g [226 mg/mmol; patients <18 years of age]) at screening.

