6.2.2. Open-Label Extension Design

Patients may be evaluated for eligibility in the open-label extension using values from the Week 108 visit as screening assessments. Patients with an eGFR <30 (but >20) mL/min/1.73 m² will be eligible for participation in the open-label extension at the discretion of the Investigator, but will require close monitoring of eGFR and serum potassium (see [Section 7.2.2](#)).

For patients who agree to participate in the open-label extension and meet eligibility criteria (see [Section 7.2](#)), the Week 112 visit will also serve as the baseline visit for the open-label extension. Standard-of-care treatment (ACEI and/or ARB therapy) will be discontinued before the Week 112 visit. The final dose of an ACEI and/or ARB should be taken on the day before the Week 112 visit. At this visit, patients will sign a new informed consent (if not completed previously) for the open-label extension and begin taking open-label sparsentan. All Week 112 evaluations must be completed prior to the first dose of open-label sparsentan.

[figure not shown]
Patients who are taking 2 or 4 capsules of study medication (ie, 400 mg or 800 mg sparsentan or 150 mg or 300 mg irbesartan) at the end of the double-blind period will initiate treatment in the open-label extension at one-half the corresponding dose of open-label sparsentan for the first 2 weeks (ie, 200 mg or 400 mg sparsentan, respectively), then titrate to the target dose after confirmation of tolerability at Week 114. Patients who are taking 1 capsule of study medication (ie, 200 mg sparsentan or 75 mg irbesartan) at the end of the double-blind period will initiate treatment in the open-label extension at 200 mg open-label sparsentan and continue on that dose

throughout the open-label extension. For details regarding dose titration in the open-label extension, see [Section 8.1.2](#); for details regarding dose modifications, see [Section 8.3.2](#).

As in the double-blind period, additional antihypertensive agents are allowed during the open-label extension to maintain blood pressure $\leq 130/80$ mmHg (patients ≥ 18 years of age) or \leq the 75th percentile (patients < 18 years of age; [Banker 2016](#)), with the exception of those that inhibit the RAAS and endothelin systems (see [Section 15.2.1](#) for concomitant medication considerations).

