10.7.2. Reporting Serious Adverse Events

The necessity and time requirements for reporting of SAEs to the Sponsor or its designee and/or regulatory agencies are as follows:

- All SAEs will be reported by email to the SAE contact on the [Study Contact Information](#) page of this protocol or by fax to the number in the Investigator Site File

- within 24 hours of the Investigator's first knowledge of the event, regardless of causal relationship.
- For the double-blind portion of the study (Day 1 through Week 112) and the open-label extension portion of the study (Week 112 and after), a completed SAE Report Form containing a detailed written description of the event along with available supporting documents (eg, discharge summary, autopsy report, diagnostic test results, etc.) will be provided by email to the SAE contact on the [Study Contact Information](#) page or by fax to the number in the Investigator Site File. For complete instructions, refer to SAE Report Form completion guidelines.
 - Additional information that is not available at the time the initial SAE Report Form was completed will be promptly reviewed and provided by email to the SAE contact on the Study Contact Information page or by fax to the number in the Investigator Site File within 48 hours of receipt. Full supporting documentation should be solicited by the investigative site even if the SAE occurred at another institution. Such documentation may include copies of relevant patient/hospital records, discharge summaries, laboratory/test results or autopsy reports.
 - If at any time after the patient has completed participation in the study (as defined in [Section 6.3.1](#) and [Section 6.3.2](#)), the Investigator or study staff becomes aware of an SAE that they suspect is related to the study medication (see [Section 10.6.1](#)), the event and any known details will be reported promptly by email to the SAE contact on the Study Contact Information page or by fax to the number in the Investigator Site File, following the reporting instructions in this section.

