
Protocol Section	Germany Text (revised text in bold)
	
the Service Provider or home care Country Coordinator as necessary to contact the patient to schedule their home care visit and will not be provided to the Sponsor. The Service Provider will communicate the date and time of the home care visit to the study site. The site must be available during the conduct of the home care visit; furthermore, the site will provide the Service Provider with an emergency phone number where the PI can be reached during the home care visit should there be the need to speak to the PI.
 
Home care visits may be implemented at Week 2, 4, 6, 8, 12, 24, 36, 48, 60, 72, 84, 96, and 108 during the double-blind treatment period of the study. Home care visits are not allowed to be utilized for screening, Day 1 (randomization), and Week 112 (end of double-blind treatment visit/first open-label extension visit). Study procedures conducted at these visits may not be delegated to the Service Provider and are required to be conducted at the site.
 
Home care visits may be implemented at Week 114, 124, 136, 148, 160, 172, 184, 196, 208, 220, 232, 244, 256, and 268 during the open-label extension treatment period of the study.
 
The PI may delegate and supervise the following study procedures to the Service Provider to be conducted during the home care visit:
 
 • Measure vital signs (blood pressure, heart rate, respiratory rate, body weight, and body temperature) • Measure orthostatic vitals (heart rate and blood pressure), as applicable. If any signs of orthostatic hypotension are observed, the Service Provider must promptly communicate this to the Investigator at site by telephone call during the visit • Collect biologic specimens (including processing, packaging, and shipment to the designated laboratory) to include the following: hematology, chemistry, chemistry with N-terminal prohormone of brain natriuretic peptide; serum pregnancy test; aldosterone, plasma renin; endothelin; pre-dose PK; quantitative urinalysis; urinalysis; urine pregnancy test; and collection of biomarker samples (serum, plasma, and urine samples). • Perform body system assessment per local regulations (only peripheral assessment allowed in European Union countries) • Perform 12-lead ECG, as applicable

Protocol Section	Germany Text (revised text in bold)

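### For patients who turn 16 between screening and Week 108, open-label eGFR change from Week 112 crosses two equations unless the Week 112 reference is recomputed, and neither document asks for that.

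*Protocol*

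**What the plan says.** Protocol 9.8, repeated in 12.7 and the synopsis, has one rule for each period. In the double-blind period, CKD-EPI applies to adults and to children of 16 or more "years of age at screening for the double-blind period, and the Modified Schwartz formula for children" under 16. In the open-label extension the cut is the same but the reference age is not: CKD-EPI applies to adults and to children of 16 or more "years of age at Week 108, and the Modified Schwartz formula for children" under 16.

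Protocol 6.1.3 lists as an open-label endpoint: "The absolute and percent change from Week 112 in eGFR at each visit". Protocol 6.2.1 describes Week 112 as the "final visit of the double-blind period 4 weeks after study medication has been discontinued (ie, Week 112"). Protocol 6.2.2 adds that "the Week 112 visit will also serve as the baseline visit for the open-label extension".

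SAP 6.5.9 uses age at screening for all baseline and post-baseline visits and has no Week 108 reset. SAP 6.4.2 takes as open-label baseline the latest available measurement up to the first open-label dose and does not mention recalculation. SAP 3.2.5 leaves the open-label endpoints to a separate SAP.

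**The concern.** A change score is interpretable only if both values are on the same scale. Fixing the equation by screening age gives each patient one equation through the double-blind period. The Week 108 reset breaks that for a child who turns 16 in between: the Week 112 reference is a Modified Schwartz value and every later value is CKD-EPI. Some of the reported open-label change would then come from the formula rather than the kidney. It would appear at the first open-label visit with an eGFR and stay in every later one. Any by-age summary of the extension would show it most clearly, because few patients would be there to dilute it.

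**Working it through.** **Which equation applies at which visit.** Take a patient under 16 at screening and 16 or older at Week 108.

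- Day 1 to Week 108: Modified Schwartz (screening-age rule).
- Week 114 onward: CKD-EPI (Week-108-age rule).
- Week 112: the text does not settle it directly. Protocol Tables 1 and 5 list it with the double-blind visits, the open-label schedule (Table 6) starts at Week 114, and SAP Table 2 includes it in the double-blind visit windows. These point to the screening-age rule and Modified Schwartz.

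A child still under 16 at Week 108 does not switch later, because the open-label age is fixed at that visit.

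**Who is affected.** Screening lasts 6 weeks and may be extended to 8 (Protocol Table 1).

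- 108 + 6 = 114 weeks; 114 x 7 / 365.25 = 2.18 years; 16 - 2.18 = 13.82.
- 108 + 8 = 116 weeks; 116 x 7 / 365.25 = 2.22 years; 16 - 2.22 = 13.78.

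The switchers are therefore about 13.8 to under 16 at screening. They must be at US or UK sites, the only ones enrolling children (Protocol 7.1.1), and must enter the extension. The documents do not give their number.

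**Size of the step.** The documents cite the two equations without coefficients, so only the form can be given. Let r be CKD-EPI divided by Modified Schwartz at the same creatinine, E the Week 112 value and f the share of open-label patients who switch. With creatinine unchanged:

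- artificial percent change in a switcher = (r - 1) x 100%
- artificial absolute change in a switcher = E x (r - 1)
- shift in the open-label mean = f x E x (r - 1)

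The values of r, E = 60 mL/min/1.73 m2 and f below are assumptions for illustration:

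| r | Percent change | Absolute change in a switcher | Mean shift, f = 1% | Mean shift, f = 5% |
|---|---|---|---|---|
| 0.8 | -20% | -12 | -0.12 | -0.60 |
| 0.9 | -10% | -6 | -0.06 | -0.30 |
| 1.0 | 0 | 0 | 0 | 0 |
| 1.1 | +10% | +6 | +0.06 | +0.30 |
| 1.25 | +25% | +15 | +0.15 | +0.75 |
| 1.5 | +50% | +30 | +0.30 | +1.50 |

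**If Week 112 is recomputed** with the Week-108-age equation for open-label change, both values are on one scale and the equation-driven step is 0.

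**Other open-label baselines.** Protocol 12.12 allows exploratory analyses from before the first double-blind dose. That value uses the screening-age equation, so it crosses the switch whichever rule governs Week 112, unless it is recomputed too.

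**The case against.** The strongest reply is that Week 112 belongs to both periods. It is the open-label baseline visit. Protocol 10.7.2 divides serious adverse event reporting into the "double-blind portion of the study (Day 1 through Week 112) and the open-label extension portion of the study (Week 112 and after"), and the Germany appendix calls the visit "Week 112 (end of double-blind treatment visit/first open-label extension visit"). Fixing age at Week 108, just before that baseline, fits an intention to use one equation from the open-label baseline onward. On that reading there is no step in change from Week 112.

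This stands as far as it shows that a step is not certain. It does not remove the problem. Week 112 also feeds double-blind secondary endpoints measured from the Day 1 baseline (Protocol 6.1.1.2). A single Week 112 value under the Week-108-age rule would move the mismatch into those endpoints. Only two Week 112 values, one per purpose, avoid both, and neither document provides for two.

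A second reply is that the detail belongs in the open-label SAP. That is fair: that document was not available and may deal with it. The present SAP is also mainly a double-blind plan, so its screening-age rule may not have been meant for open-label eGFR. The protocol text still needs an explicit answer, and the two rules still need to be reconciled.

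A reader might also infer that the step is an apparent gain that flatters open-label sparsentan. The documents do not support this. They contain no coefficients, so neither the sign nor the size can be derived from them.

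**Conclusion.** The concern holds as a conditional one. Under the stated rules, and with Week 112 treated as a double-blind visit, patients who turn 16 between screening and Week 108 have open-label eGFR change measured across two equations. The artificial part is (r - 1) x 100% in each such patient, with r unknown from the documents.

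The effect on overall open-label means is likely to be small. At an assumed eGFR of 60 and f of 1% to 5%, it is 0.06 to 0.30 mL/min/1.73 m2 in absolute size for r = 0.9 or 1.1, and 0.30 to 1.50 for r = 1.5. For the individual adolescent, or in a paediatric summary, it could be large relative to any real change.

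A reader might infer that the trial's main results are affected. They are not: each patient has one equation throughout the double-blind period, so the primary and secondary double-blind endpoints are untouched as long as Week 112 keeps the screening-age equation for them. Open-label endpoints are summarized descriptively (Protocol 12.12). This is a minor point, worth fixing because the correction is so cheap.

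**What to change.** State in the protocol or the open-label SAP that, for open-label eGFR change, the Week 112 reference and any earlier baseline used in open-label analyses are recomputed from stored creatinine with the equation assigned at Week 108. State also that the screening-age value at Week 112 is kept for the double-blind endpoints. Say explicitly that the screening-age rule in SAP 6.5.9 does not govern open-label visits, so that it agrees with the protocol.

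The cost is a sentence or two and two derived Week 112 values for a few patients. No new data are needed: creatinine is measured at each of these visits, and the SAP mentions height only for Modified Schwartz.

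Keeping the screening-age equation through the extension would also remove the step, but is less attractive. A patient just under 16 at screening would reach about 21 by the end of the study (6 + 268 = 274 weeks, or 5.25 years). Scheduled height measurement stops at 18 (Protocol 9.6), so a height-based formula would then run on a carried-forward height.
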